the Investigator does not need to actively monitor the subject for AEs but should only report relevant SAEs and relevant AESIs of which the Investigator may become aware of.

The REP for BI 433651 is defined as 30 days after the last trial medication application. All AEs which occurred through the treatment phase and throughout the REP will be considered as on treatment, please see [Section 7.3.4](#). Events which occurred after the REP and before trial termination date will be considered as follow-up events.

AE reporting to sponsor and timelines

The Investigator must report SAEs, AESIs, and non-serious AEs which are relevant for the reported SAE or AESI, on the BI SAE form via fax immediately (within 24 hours) to the sponsor's unique entry point (country specific contact details will be provided in the ISF). The same timeline applies if follow-up information becomes available. In specific occasions the Investigator could inform the sponsor upfront via telephone. This does not replace the requirement to complete and fax the BI SAE form.

With receipt of any further information to these events, a follow-up SAE form has to be provided. For follow-up information the same rules and timeline apply as for initial information.

Information required

For each AE, the Investigator should provide the information requested on the appropriate CRF pages and the BI SAE form. The Investigator should determine the causal relationship to the trial medication and any possible interactions between the investigational drug and a Non-Investigational Medicinal Product (NIMP).

The following should also be recorded as an (S)AE in the CRF and SAE form (if applicable):

- Worsening of the underlying disease or of other pre-existing conditions
- Changes in vital signs, ECG, physical examination and laboratory test results, if they are judged clinically relevant by the Investigator.

If such abnormalities already pre-exist prior trial inclusion they will be considered as baseline conditions.

All (S)AEs, including those persisting after individual subject's end of trial must be followed up until they have resolved, have been sufficiently characterised, or no further information can be obtained.

Pregnancy

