Adverse events will be coded using the Medical Dictionary for Regulatory Activities (MedDRA). Frequency, intensity and causal relationship of AEs will be tabulated by treatment, primary system organ class and preferred term. SAEs, AESIs ([see Section 5.3.10.1](#)) and other significant AEs (according to ICH E3) will be listed separately.

Laboratory data will be analysed both quantitatively as well as qualitatively. The latter will be done via comparison of laboratory data to their reference ranges. Values outside the reference range as well as values defined as clinically relevant will be highlighted in the listings. Treatment groups will be compared descriptively with regard to distribution parameters as well as with regard to frequency and percentage of subjects with abnormal values or clinically relevant abnormal values.

Vital signs, physical examinations, or other safety-relevant data observed at screening, baseline, during the course of the trial, follow-up period and at the end of trial evaluation will be assessed with regard to possible changes compared to findings before start of treatment. Baseline refers to the last measurement before drug administration.

The ECG variables QT, HR, QTcF, QTcB, PR, QRS, and RR obtained from the centralised evaluation of 12-lead ECG recordings will be the basis for the derivation of quantitative and categorical ECG endpoints. These endpoints and their analyses will be described in the TSAP.

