3. INTRODUCTION

As per International Council for Harmonisation of Technical Requirements for Pharmaceuticals for Human Use (ICH) E9 ([10](#)), the purpose of this document is to provide a more technical and detailed elaboration of the principal features of the analysis described in the revised Clinical Trial Protocol (CTP), and to include detailed procedures for executing the statistical analysis of the primary and secondary variables and other data.

This Trial Statistical Analysis Plan (TSAP) assumes familiarity with the revised CTP. In particular, the TSAP is based on the planned analysis specification as written in CTP Section 7 “Statistical Methods and Determination of Sample Size”. Therefore, TSAP readers may consult the CTP for more background information on the study, e.g., on study objectives, study design and population, treatments, definition of measurements and variables, planning of sample size, randomisation.

Within the earlier version 2.0 of the TSAP, the planned analyses for the healthy volunteer (HV) cohort has been specified. All descriptions and planned analyses for this trial part are based on CTP Version 6.0 (20 April 2017) even though part 1 was conducted according to CTP Version 3.0 (01 December 2016) which was applicable when recruitment for part 1 started. Planned analyses for CF subjects were described as detailed as possible in version 2.0 of the TSAP. At the time of recruitment of the first CF subjects for part 2 of the study, CTP Version 7.0 (06 September 2017) was applicable and the CTP was amended to Version 8.0 (09 November 2017) during conduct of part 2. Within the current revised version of the TSAP the planned analyses for the CF subjects were updated or added based on CTP Version 8.0. For further details refer to [Section 4](#).

Study data will be stored in a trial database within the Oracle ClinicalTM system.

The statistical analyses will be performed within the validated working environment CARE (Clinical data Analysis and Reporting Environment), including SASTM (current Version 9.4, by SAS Institute Inc., Cary, NC, USA), and a number of SASTM-based tools (e.g., macros for the analyses of adverse event (AE) data or laboratory data; Report Appendix Generator system (RAGe) for compilation/formatting of the clinical trial report (CTR) appendices).

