7.8.2 Laboratory data

The analyses of laboratory data will be descriptive in nature and will be based on BI standards (6). If possible, analyses for HV will be based on original values. If multiple reference ranges apply for one parameter (e.g. due to different age groups) for HV, analyses will be based on normalised values, which means transforming to a standard unit and a standard reference range. Analyses for CF subjects will be based on normalized values. If references ranges are not available, analyses will be based on original values.

Laboratory data will be analysed both quantitatively as well as qualitatively. The latter will be done over comparing laboratory data to their reference ranges. Values outside the reference range will be highlighted in the listings.

Dose groups will be compared with descriptive statistics of laboratory values over time and by analysing differences from baseline (see [Section 6.7](#) for definition of baseline).

Additionally, frequency tables of changes between baseline and last values on treatment with respect to the reference ranges will be presented. For electrolytes, descriptive statistics of values over time and differences from baseline will be provided comparing all active doses versus placebo for HV. Furthermore graphical representations over time will be generated for serum electrolytes for HV and CF subjects and for urine electrolytes for HV subjects.

Clinically relevant findings in laboratory data will be reported as AEs and will be analysed as part of AE analysis.

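### SAP 7.8.2 narrows the protocol's count of subjects with abnormal laboratory values to a last-value shift table and names no count of clinically relevant values

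*SAP*

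**What the plan says.** Protocol 7.3.4 plans two displays for laboratory data beyond the summary statistics. The first is a descriptive comparison of treatment groups by "frequency and percentage of subjects with abnormal values or clinically relevant abnormal values". The second is a rule for the listings: "Values outside the reference range as well as values defined as clinically relevant will be highlighted in the listings".

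SAP Section 3 states that "the TSAP is based on the planned analysis specification as written in CTP Section 7". SAP 7.8.2 then gives the listing rule as "Values outside the reference range will be highlighted in the listings", without the clinically relevant values. Its only table of counts is described as "frequency tables of changes between baseline and last values on treatment with respect to the reference ranges will be presented". It adds descriptive statistics over time and electrolyte plots. On clinically relevant values it says "Clinically relevant findings in laboratory data will be reported as AEs and will be analysed as part of AE analysis".

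Whether a laboratory change becomes an AE is settled in Protocol 5.3.10.2, which asks sites to record "Changes in vital signs, ECG, physical examination and laboratory test results, if they are judged clinically relevant by the Investigator". No numeric rule is attached.

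SAP 7.8.2 also refers to a sponsor standard for laboratory displays (SAP reference 6), whose content is not in either document.

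**The concern.** A count of subjects with at least one abnormal value treats every arm by the same rule. The SAP leaves two partial substitutes. One is a table that looks at a single late time point. The other is an AE count that depends on each investigator's judgement, at one healthy-volunteer site and at least 6 CF sites.

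This matters most for serum potassium. Protocol 2.3.2 names serum electrolyte change, and a rise in potassium in particular, as the one systemic toxicity to be expected. It plans frequent electrolyte sampling for that reason. If the samples taken during dosing do not reach a by-treatment count, the tables say least about the period when the effect is most likely.

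SAP Section 4 has a list for changes that did not come from a protocol amendment, and it records even the added FEV₁/FVC ratio there. The visible text does not mention the laboratory change, so a reader comparing the report with the protocol would not know that a planned display had been altered.

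**Working it through.** The plan gives no figure to reproduce. The check compares the two texts and applies the SAP's analysis phases to the sampling schedule.

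**1. What each document names**

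| Display | Protocol 7.3.4 | SAP 7.8.2 |
|---|---|---|
| Out-of-range values flagged in listings | yes | yes |
| Clinically relevant values flagged in listings | yes | not named |
| Subjects with abnormal values, n and % | yes | baseline-to-last-value shift only |
| Subjects with clinically relevant values, n and % | yes | not named; AE route only |

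**2. On-treatment window, healthy volunteers.** SAP 6.1 and Table 6.1: 1, which covers laboratory tests, run the phase to the end of the residual effect period (REP), 30 days after the last dose. Protocol 4.1.4 puts the last dose on Day 7. End of REP = 7 + 30 = Day 37.

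**3. Serum electrolytes, healthy volunteers.** Flow Chart I, footnote 8, lists Days 1, 2, 3, 4, 5, 6, 7, 8, 16, 23 and 30. Day 1 is pre-dose and serves as baseline, which leaves 10 post-baseline days. End of study is Day 37 to 44.
- End of study on Days 38 to 44: the last on-treatment value is Day 30, which is 30 − 7 = 23 days after the last dose. Days 2, 3, 4, 5, 6, 7, 8, 16 and 23 do not enter the table: 9 of 10.
- End of study on Day 37: that sample is the last value, and 10 of 11 do not enter.
- In both cases none of the samples from Days 2 to 7, the dosing days, is used.

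**4. Full laboratory panel, healthy volunteers.** After dosing starts, Flow Chart I marks the full panel only on Day 7 and at end of study. If end of study is after Day 37, Day 7 is the last scheduled on-treatment value and does enter the shift table. The loss in step 3 is therefore specific to electrolytes, apart from an end of study on Day 37 or an unscheduled repeat.

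**5. CF subjects.** Last dose on Day 14, so end of REP = 14 + 30 = Day 44. With the minimum 30-day washout, period 2 Day 1 is also Day 44, and its Day −7 to −3 laboratory visit falls on Days 37 to 41. The last on-treatment value for period 1 can then be a period 2 baseline sample, subject to the blinded review in the footnote to Table 6.1: 2. The laboratory cells of Flow Chart II are not legible enough to count sampling days.

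**6. Other routes into a count**
- *AE:* needs the investigator's judgement. After premature discontinuation of medication, Protocol 5.3.10.2 requires only related SAEs and related AESIs from subjects who stay in the trial.
- *Hepatic AESI (Protocol 5.3.10.1):* needs ALT or AST at least 3 times ULN with total bilirubin at least 2 times ULN, or ALT or AST at least 10 times ULN.
- *Potassium withdrawal (Protocol 3.3.4):* needs a confirmed value of at least 5.5 mmol/L. Under Protocol 5.3.7, local results guide dosing but are not entered in the database, so a high central value need not coincide with a withdrawal.

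**7. Size of one uncounted subject.** 1/8 = 12.5% of a healthy-volunteer dose group. Pooled placebo is also 4 × 2 = 8. In Part 2, 1/24 = 4.2% per treatment.

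**The case against.** Much can be said for the SAP.

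- A reader might infer that the count of abnormal values has been dropped and handed to AE reporting. The documents do not support that. The shift table is a count against reference ranges, and Protocol 7.3.4 does not say that its count must cover any time on treatment. The count is narrowed.
- A reader might also infer that a raised ALT on Day 7 that later normalises is counted nowhere. For healthy volunteers this generally fails, as step 4 shows, although the table would record it only as out of range.
- Excursions are not invisible. SAP Section 7 puts Min and Max in every continuous summary, so a value that is the extreme of its group at a visit can be seen. Out-of-range values are flagged in the listings, and electrolytes are plotted. These displays stand, but none is a count of subjects by treatment.
- The potassium limit has its own consequences. A confirmed value leads to withdrawal with a reported reason, and two active subjects at one dose level meet a discontinuation criterion in Protocol 3.3.4.1. This covers the most serious cases only.
- Neither document defines a clinically relevant laboratory value numerically, so investigator-reported AEs are one possible reading of 7.3.4. Against that, the protocol refers to values *defined* as clinically relevant and counts them separately from AEs.
- The sponsor's laboratory standard may supply the table, and nothing in the SAP rescinds the protocol sentence. This cannot be settled from the documents.

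**Conclusion.** The point holds in limited form. SAP 7.8.2 does not carry over the protocol's comparison in full, and the visible Section 4 does not say so. The abnormal-value count becomes a baseline-to-last-value table, and clinically relevant values have no named count or flag of their own. The clearest consequence is in healthy-volunteer serum electrolytes, where 9 of 10 scheduled post-baseline days up to Day 30, and every sample during dosing, stay outside the table. A transient abnormality that is not an AE, AESI or withdrawal may appear in no summary count.

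This rests on complete data, on the SAP 6.1 phases defining the last on-treatment value, and on the schedule in the current Flow Chart I (SAP Section 3 says Part 1 was run under protocol version 3.0). It also assumes that the unseen sponsor standard does not already require the table. The documents do not show that any abnormality will in fact be missed.

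The analysis is descriptive and no hypothesis depends on it. It should still be corrected, because it concerns the main expected systemic risk and the data are already held.

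**What to change.** In SAP 7.8.2 add, for each parameter and treatment, the number and percent of subjects with:
- at least one on-treatment value outside the reference range; and
- at least one on-treatment value meeting a clinically relevant criterion that the sponsor fixes before unblinding. This would be the criterion in its own laboratory standard, if there is one, plus the potassium limit already in the protocol, used here only for tabulation and applied to central values in original units. CF analyses otherwise use normalised values.

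Show the dosing days separately from the REP. Flag both kinds of value in the listings, and keep the AE route alongside.

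SAP Section 4 speaks of the Part 1 analysis in the past tense. If those data are already unblinded, use only criteria that predate unblinding and label the Part 1 table as added.

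If the cited sponsor standard already produces this table, naming it in 7.8.2 is enough. If the sponsor prefers the narrower analysis, Section 4 should declare and justify it.

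The cost is SAP wording and one extra standard table per trial part. No new data are needed.

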7.8.3 Vital signs

The analyses of vital signs will be descriptive in nature. Descriptive statistics of vital signs over time and for the changes from baseline (see Section 6.7) will be provided.

Clinically relevant findings in vital signs data will be reported as AEs and will be analysed as part of AE analysis.

7.8.4 ECG

Abnormal findings in 12-lead ECG or continuous ECG monitoring will be reported as baseline conditions (at screening) or as AEs (during the trial) if judged clinically relevant by the investigator.

The evaluation of 12-lead ECG data will be based on the TS.

Listing of individual data

For all quantitative endpoints, listings of individual data will be shown in Appendix 16.2. Occurrences of notable findings will be flagged. For all subjects with any notable finding of quantitative ECG recordings, a separate listing will be created as end-of-text display (same display as in Appendix 16.2), and the corresponding time profiles will be shown. Comments regarding the ECGs will be listed.

Analysis of central tendency

For quantitative ECG endpoints (RR, PR, QRS, QT, HR, QTcF and QTcB) descriptive statistics for absolute values and absolute changes from baseline will be provided for HV and CF subjects.

For QTcF, QT and HR of HV, a repeated measurements analysis of the changes from baseline with baseline as a covariate will be performed. The model will include the fixed effects “base”, “dose group”, “base*time” interaction, and “dose group*time” interaction. The covariance model for the repeated effect “time” will be unstructured. For each dose group and each time point, the contrast of the means for “treatment-placebo” will be estimated by the difference in the corresponding adjusted means (Least Squares Means); two-sided 90% CIs based on the t-distribution will also be computed. For each of the above ECG variables, the time profiles of the mean differences to placebo in the changes from baseline and the corresponding 90% CIs will be presented in a figure.

For QTcF, QT and HR of CF subjects, a repeated measurements analysis of the changes from baseline with subject and period baseline as covariates will be performed, if feasible, for time-points defined in CTP Version 8.0:

The model will include the fixed effects “base 1” as the subject baseline (i.e. the arithmetic mean of the respective period baselines per subject), “base2” as the period baseline, “treatment”, “time”, “Period”, “base1*time” and “base2*time” interaction, “period*time” interaction, and “treatment*time” interaction. Subject is included as a random effect on the intercept. The covariance model for the repeated effect “time” will be unstructured, using the blocking factor ‘subject-by-period’. For each time point, the contrast of the means for “treatment-placebo” will be estimated by the difference in the corresponding adjusted means (Least Squares Means); two-sided 90% CIs based on the t-distribution will also be computed. For each of the above ECG variables, the time profiles of the mean differences to placebo in the changes from baseline and the corresponding 90% CIs will be presented in a figure.

Categorical Endpoints

For the categorical endpoints, frequency tables will be provided.

Categorical endpoints will also include morphological findings that might be attributable to treatment. In particular, new onsets of findings not present at baseline will be explored. A morphological finding observed on treatment that was not reported at baseline will be categorized as a ‘new onset’ of this finding.

For subjects with notable findings, the individual time courses of RR, PR, QRS, QT, HR, QTcF and QTcB of these subjects will be presented in figures.

